4 INVESTIGATIONAL PLAN

4.1 Overall Study Design

This is a multicenter, open-label, long-term extension study to evaluate the safety and tolerability of oral AERT in patients with spasticity due to MS. Subjects from the double-blind study (Study OSS440-3004) may rollover into this open-label extension study, as well as *de novo* subjects, provided that all inclusion and none of the exclusion criteria are met. Eligible *de novo* subjects will undergo a washout period withdrawing all medications used for anti-spasticity and/or muscle relaxation up to 21 days prior to enrolling in this open-label study. There will be a 9-day titration period, then a 52-week maintenance period, followed by a 2-week taper period. Figure 1 presents the timeline diagram for the study. Figure 2 presents the open-label dosing regimen flowchart, including titration and taper doses, to be used during the study. Once the subject has reached the maintenance dose, they will remain on that dose for approximately 1 year. The maintenance dose will be the highest tolerated dose not exceeding 80 mg per day. Table 1 presents the schedule of assessments, including study visits and weeks, for the study.

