7.4. Planned Study Analyses

7.4.1. Statistical Summaries: Descriptive and Inferential

No statistical tests will be performed in this study.

Descriptive summaries of variables will be provided where appropriate. For continuous variables, the number of non-missing values (n) and the median, mean, standard deviation, minimum, and maximum will be tabulated. For categorical variables, the counts and proportions of each value will be tabulated. Expansion of descriptive table categories may occur if such elaborations are thought to be useful.

For the summary statistics of all numerical variables unless otherwise specified, minimum and maximum will be displayed to the same level of precision as reported. Mean and median will be displayed to one level of precision greater than the data collected. The standard deviation / standard error will be displayed to two levels of precision greater than the data collected.

Change from baseline scores will be calculated as the post-baseline measurement minus the baseline value.

Unless otherwise specified, all tables will be presented by Modal Dose of 40 mg, 60 mg, 80 mg, and Overall group.

All collected data will be presented in listings. Data not subject to analysis according to this plan will not appear in any tables or figures but will be included in the data listings.

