8.6. Treatment Compliance

The total number of days at each unique dose level and overall will be summarized.

Dosing information, including date of administration, and days at each unique dose level will be listed by subject.

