10. SAFETY ANALYSES

10.1. Adverse Events

The number and percent of subjects with any treatment-emergent adverse events (TEAEs) will be displayed by system organ class and preferred term (MedDRA Version 20.1). Within each preferred term, subjects will be counted only once if they had more than one event reported during the treatment period.

TEAEs will also be summarized by greatest reported severity for each event preferred term. Counts indicate subjects reporting one or more TEAEs that map to the severity grade classification for each preferred term. At each level of summarization (system organ class or event preferred term) subjects are only counted once and the worst severity case of repeated instances of the same TEAE will be used in tabulations. TEAEs will also be summarized by strongest investigator assessment of relationship to study drug in a similar manner.

In addition to the above described analyses, specific AE summaries will be presented under the following conditions:

- TEAEs by SOC/PT will be presented by modal dose within period (titration/dose response, maintenance, and taper period).

- TEAEs by SOC/PT will be presented by dose the subject was on at time of event within period (titration/dose response, maintenance, and taper period).
- All AE summaries will be presented by dose the subject was on at time of event.

Analyses of AEs will be performed for those events that are considered treatment emergent, where treatment emergent is defined as any AE with onset or worsening on or after the first dose of study drug up until last dose of study drug.

Treatment emergent summarization will be characterized by serious or not, the severity and the relationship with the study drug. A conservative approach will be taken to assess the relationship of an AE to study drug; if the relationship of an event is missing, it will be considered treatment-related. Missing severity will be coded as severe.

All TEAEs will be listed individually by subject. In addition, a separate listing will be produced for AEs that are not treatment-emergent.

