10.2.2. Serious Adverse Events

The number and percent of subjects with Treatment Emergent Serious Adverse Event (TESAE) will be displayed by system organ class and preferred term, and relationship to study drug. Within each preferred term, subjects will be counted only once if they had more than one TESAE event reported during the treatment period.

Clinical narratives for each TESAE observed will be written to include important data and safety findings related to the individual TESAE and included in the final clinical study report.

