11.2 Population Summary Conventions

- Population(s) represented on the tables or data listings will be clearly identified in the last title of the Table as “Population: <name of population>” and will be identical in name to that identified in the protocol or SAP.
- Consistent terminology will be used to define and identify a population.
- Sub-population(s) or special population(s) descriptions will provide sufficient detail to ensure comprehension of the population (e.g., FAS Females, Per-Protocol Males >60 years of age) used for analysis in a table or figure.
- Population sizes may be presented for each treatment or dosing category as totals in the column header as (N=xxxx), where appropriate.
- Population sizes shown with summary statistics are the samples sizes (n) of subjects with non-missing values.
- All population summaries for categorical variables will include all categories that were planned and for which the subjects may have had a response. Percentages corresponding to null categories (cells) will be suppressed.
- All population summaries for continuous variables will include: N, mean, SD, minimum, and maximum. Other summaries (e.g. number missing, median, quartiles, 5%, 95% intervals, CV or %CV) may be used as appropriate.
- All percentages are rounded and reported to xx.x%. A percentage of 100% will be reported as 100%. No value of 0% will be reported. Any computation of percent that results in 0% is to be presented as a blank.
- Population summaries that include p-values will report the p-value to four decimal places with a leading zero (0.0001). All p-values reported on default output from statistical software (i.e., SAS[®] Software version) may be reported at the default level of precision. P-values <0.0001 should be reported as <0.0001 not 0.0000.

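### AE percentages by dose at time of event have no stated denominator and no person-time, so unequal time at each dose can look like a dose effect

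*SAP*

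**What the plan says.** SAP 10.1 specifies the number and percent of subjects with TEAEs, each subject counted once per preferred term over the treatment period. It then adds three sets of tables. One is by modal dose within period. One is by dose at event within period: "TEAEs by SOC/PT will be presented by dose the subject was on at time of event within period (titration/dose response, maintenance, and taper period". The third has no period split: "All AE summaries will be presented by dose the subject was on at time of event".

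An event is treatment emergent if its onset or worsening falls "on or after the first dose of study drug up until last dose of study drug", so days in the final taper count. Serious events follow the same pattern in SAP 10.2.2: "The number and percent of subjects with Treatment Emergent Serious Adverse Event (TESAE) will be displayed by system organ class and preferred term". SAP 10.2.3 does likewise for events leading to discontinuation or interruption.

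The nearest text to a denominator is in three places:

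- SAP 7.4.1 sets the default columns: "Unless otherwise specified, all tables will be presented by Modal Dose of 40 mg, 60 mg, 80 mg, and Overall group".
- SAP 11.2 makes column sizes optional: "Population sizes may be presented for each treatment or dosing category as totals in the column header as (N=xxxx), where appropriate".
- SAP 7.1.2 defines one safety population, with no rule per dose.

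Protocol 11.5 adds neither a denominator nor person-time. Exposure by dose appears only in SAP 8.6: "The total number of days at each unique dose level and overall will be summarized". No AE table refers to it.

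On the schedule, Protocol 4.1 states: "There will be a 9-day titration period, then a 52-week maintenance period, followed by a 2-week taper period". Protocol 7.5 divides the titration into 3 days each at 40, 60 and 80 mg/day.

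**The concern.** In a table by dose at event, one subject can contribute to several columns. The percentage in a column depends on who is in its denominator and on how long those subjects were at risk at that dose. The SAP settles neither. It also does not say whether a subject with the same preferred term at two doses counts once in the table or once in each column.

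Time at dose is unequal by design. Nearly all follow-up of a subject maintained at 80 mg is at 80 mg, while stays at the lower doses last days. A crude percentage then reflects time at dose as well as any effect of dose.

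The primary objective is long-term safety, and the study is meant to supply it at 80 mg/day. SAP 3.2 foresees use of the results in regulatory submissions and manuscripts. A reader who takes the 40, 60 and 80 mg columns at face value could see a dose gradient that exposure alone has produced.

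**Working it through.** The documents give no AE rate and no statistical basis for the sample size, so there is no planned figure to reproduce. The calculation asks what the tables would show if dose had no effect.

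**From the documents.** Titration of 3 days at each dose (Protocol 7.5), 52 weeks = 364 days of maintenance (Protocol 4.1), a 2-week final taper, and no taper for subjects who only ever reach a 40 mg maintenance dose (Protocol 7.1.1).

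**Assumed.** Same constant hazard at every dose, one-year risk 60%, no dropout, and all subjects complete titration and are then held at their dose. The taper is 7 days at 60 and 7 at 40 mg from 80 mg, and 7 days at 40 mg from 60 mg (the dosing flowchart is not shown). The mix at 40/60/80 mg is 10/10/80% or 20/20/60%.

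**Formula.** h = −ln(0.4)/365.25 = 0.0025087 per day; f(d) = 1 − exp(−h·d). This gives f(3) = 0.75%, f(7) = 1.74%, f(10) = 2.48%, f(350) = 58.4%, f(364) = 59.9%, f(367) = 60.2%.

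**Days at dose.** At 40 mg: 3 + 364 = 367 for subjects held there, 3 + 7 = 10 for all others. At 80 mg: 3 + 364 = 367 for subjects held there, 3 for all others. Everyone receives every dose, so the all-treated and ever-on-dose denominators coincide.

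**Tables without a period split**

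| Mix 40/60/80 | 40 mg column | 80 mg column | 80:40 |
|---|---|---|---|
| 10/10/80% | 0.1·f(367) + 0.9·f(10) = 8.25% | 0.8·f(367) + 0.2·f(3) = 48.3% | 5.9 |
| 20/20/60% | 0.2·f(367) + 0.8·f(10) = 14.0% | 0.6·f(367) + 0.4·f(3) = 36.4% | 2.6 |

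With one-year risk from 5% to 80%, the same formulas give 6.4 to 5.4 and 2.7 to 2.5.

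**Dropout.** Suppose dropout after titration is exponential, leaves 17% at one year (k = −ln(0.17)/365.25 = 0.00485 per day), and every leaver tapers. In place of f(367), the chance of an event at the maintained dose is 1 − exp(−3h)·[k/(h+k)·(1 − E) + E], with E = exp(−364(h+k)), which is 32.3%. The columns become 5.46% v 26.0% (ratio 4.8) and 8.43% v 19.7% (2.3).

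**Within-period tables.** In titration, time is 3 days at each dose for those who complete it, so the ratio is 1.0. In maintenance, with subjects on that dose in the period as denominator and doses held, it is f(364)/f(364) = 1.0. Now let a share q of the 80 mg subjects in the 10/10/80% mix have one reduction, with 7 days at 60 and 7 at 40 mg (assumed):

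- 40 mg: [0.1·f(364) + 0.8q·f(7)]/(0.1 + 0.8q)
- 80 mg: (1 − q)·f(364) + q·f(350)

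| q | 40 mg | 80 mg | 80:40 |
|---|---|---|---|
| 10% | 34.0% | 59.7% | 1.75 |
| 20% | 24.1% | 59.6% | 2.5 |
| 30% | 18.8% | 59.4% | 3.2 |

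**Person-time.** Under a constant hazard every column returns 100 × 365.25h = 91.6 per 100 person-years, which only restates the assumption. If the hazard is 10 times higher in days 1–14 with the same one-year risk (10/10/80%, subjects held at a lower dose never taking 80 mg), the pooled rates are 147 at 40 mg and 88 at 80 mg, a ratio of 0.60. A pooled rate can mislead in the other direction, so rates also need the period split.

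**The case against.** Much is already in place. The dose-at-event tables are additions to a default set by modal dose and Overall, in which each subject sits in one column. The same SAP revision that added them also added the summary of days at each dose, so a reader of the report can find exposure by dose. The within-period tables balance titration, and balance maintenance when doses are held. No tests are planned and comparing doses is not an objective. The mix, risk, taper split and absence of dropout are all assumed. Rates are not clean either: they do not remove early clustering of events or selection when dose is reduced because of an AE, and cells for rare terms will be sparse.

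Most of this stands, and it limits the severity. It does not close the gap. The days in SAP 8.6 are totals, not tied to any AE table or to time to first event. The period split is planned only for TEAEs by SOC and preferred term, not for the severity, relationship, serious or discontinuation summaries. Protocol 7.1 and 7.4 allow up to three tapers for tolerability, so short stays at a lower dose during maintenance are foreseen. Dropout lowers the ratios when early leavers take the 2-week taper the protocol asks for, but the gradient remains.

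**Conclusion.** The concern holds as a reading risk in descriptive tables, of minor to moderate severity. With no true dose effect, the tables not split by period would show an 80:40 ratio of about 5.9 (10/10/80% mix) or 2.6 (20/20/60%) under the stated assumptions, and less with dropout followed by taper. Within maintenance the ratio is 1.0 if doses are held, and 1.75 to 3.2 if 10% to 30% of 80 mg subjects have one short reduction.

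A reader might infer three stronger things that the documents do not support:

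- **Much larger ratios.** Figures of 7.2 and 4.3 arise only if subjects held at a lower dose never take 80 mg and so drop out of that denominator. That is at odds with a titration that runs through 80 mg, although some subjects may not reach it. About 24 is f(367)/f(10), the limiting case in which everyone completes at 80 mg.
- **A reversed gradient.** Dividing by the modal-dose group size can reverse the direction, but this is a strained reading. SAP 10.1 lists dose at event separately from modal dose, and that divisor can pass 100%. At an assumed 2 events per person-year without taper, it gives 30.4/30 = 101% in the 40 mg column.
- **A flawed primary safety analysis.** No error rate is at stake, and the modal-dose and Overall summaries do not carry this artefact.

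**What to change.** In SAP 10.1 and 10.2, for AE tables by dose at time of event:

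1. Define the denominator as subjects who received that dose, and in the period tables as those who received it in that period.
2. State that a subject counts once per preferred term per dose column, at the first such event at that dose.
3. Using the days derived for SAP 8.6, show person-years at that dose up to the first such event at that dose. Give the exposure-adjusted rate per 100 person-years beside the crude percentage, by period, at least for any TEAE, each SOC and common preferred terms.
4. Footnote the severity, relationship, serious and discontinuation tables: pooled percentages are not adjusted for time at dose, and rates do not remove early-onset clustering or selection from AE-driven dose reduction.

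The cost is SAP wording, modest programming, wider tables and sparse cells for rare terms.

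Separately, Protocol 7.1 (over 9 days) and 7.1.1 (20 mg per week) differ on the in-study taper. These passages must be reconciled.

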9.6.2 Urinary Symptom Profile[®] Questionnaire

The USP is a health-related quality of life questionnaire developed in 2005 by the French Association of Urology and validated in 2008 ([Haab et al 2008](#)). It is composed of 13 items in 3 dimensions to assess urinary symptoms among adults (both men and women) with stress, urge, overactive bladder, or urinary obstructive symptoms. It is administered with a time frame over the past 4 weeks. The USP is a valuable tool for self-administration by the subject to complement clinical measures and diagnosis due to it being a valid and reliable questionnaire providing comprehensive evaluation of all urinary disorders and their severity. It also allows the pathology screening and contributes to the differential diagnosis of these symptoms. Due to the potential risk of arbaclofen to produce urinary problems, mainly at the bladder level (as seen in some animal toxicological studies; see the current arbaclofen Investigator's Brochure [IB]), the utilization of this questionnaire has been implemented in the context of this study to monitor urinary symptomatology and rule out any complication that could be developed during the course of the study. An increase of 4 points in the total USP score from the previous visit will be considered an AE.

The USP questionnaire will be completed by the subject at the visits specified in Table 1. The USP is provided in Appendix 6.

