9.7.3 Reporting Adverse Events

Adverse events that occur from the time of informed consent through completion of the last study visit should be reported. Any AE that the investigator becomes aware of that occurs within 30 days of study completion or withdrawal should also be reported.

Any SAEs occurring in a subject receiving study medication must be reported to the Sponsor within 24 hours of the site being informed of the event, even if the event does not appear to be drug-related. This reporting must be done by faxing the appropriate completed form (SAE form or Exposure during Pregnancy form) to the Sponsor. Any pertinent follow-up information should be provided in a similar manner. Contact information is provided below:

Additional PSI-CRO international safety reporting lines are provided in Appendix 7.

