11.5 Safety Endpoints

Safety endpoints will be reported on the Safety population. Subjects will be reported according to the treatment they actually received. Safety assessment will be based on descriptive statistics and individual subject listings. No statistical tests will be performed for any of the safety assessments.

All reported AEs will be mapped to the Medical Dictionary for Regulatory Activities (MedDRA) system organ classifications (SOCs) and preferred terms (PTs). If a subject reports multiple events of a single PT, the greatest severity and strongest investigator assessment of relationship to study treatment will be assigned to that PT. Should an event have a missing severity or relationship, it will be classified as having the highest severity and/or strongest relationship to study drug. Summaries of treatment-emergent AEs (TEAEs) will include any AEs reported beginning with the first dose of study treatment on Day 1. The occurrence of TEAEs will be summarized by treatment group using SOCs, PTs, and severity. Separate summaries of treatment-emergent SAEs, TEAEs considered related to study treatment, and events leading to the discontinuation of study drug will be generated.

Descriptive summaries of vital signs, clinical laboratory results, USP results, and the C-SSRS results will be presented by study visit and treatment group. The number and percentage of subjects with treatment-emergent clinical laboratory abnormalities will be summarized by treatment group. Normal range clinical laboratory shifts from baseline to end of study will be summarized by treatment group.

Concomitant medications will be coded using the World Health Organization (WHO) dictionary. These data will be summarized by treatment group. Previous and concomitant medications will be presented in a data listing.

Subject disposition will be presented for all subjects. The numbers of subjects who complete the study and who discontinue early from the study will be provided. The reasons for early discontinuation will also be presented.

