3.3. Summary of Statistical Analysis Changes to the Protocol

The analyses described in this analysis plan are consistent with the analyses described in the study protocol.

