12 REVISION HISTORY

Changes from version SAP.00: The SAP was revised and amended to remove the 30 day window for the derivation of treatment emergent adverse events. Adverse events will now be counted as treatment emergent up until the last dose date.

Changes from version SAP.01: The SAP was revised and amended to add additional Adverse event analyses: All AE analyses by dose the subject was on at time of event; TEAEs by SOC/PT by modal dose and period (titration/dose response, maintenance, and taper period); TEAEs by SOC/PT analyses by dose the subject was on at time of event and period (titration/dose response, maintenance, and taper period).

For TNmAS-MAL and TNmAS-TL, the baseline from OS440-3004 will be included as a separate analysis to the planned analyses using the baseline of Visit 6/ET result from Study OS440-3004.

For dose exposure, the total days at each particular dose level have been added to the subject listing and a new summary table counting the total days at each dose level and overall has been included.

For all tables modal dose categories have been changed from < 80 and = 80 mg to modal dose categories of 40 mg, 60 mg, and 80 mg.

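### The AE analysis window closes at the last dose, so AEs and non-fatal SAEs that start in the four-week post-taper follow-up are listed but never tabulated, and SAP 3.3 does not declare the change

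*SAP*

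**What the plan says.** SAP 10.1 restricts AE analyses to treatment-emergent events, meaning "any AE with onset or worsening on or after the first dose of study drug up until last dose of study drug". Its by-period tables cover titration, maintenance and taper, and nothing later. For everything else: "In addition, a separate listing will be produced for AEs that are not treatment-emergent".

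The SAE outputs follow the same definition. SAP 10.2.2 tabulates treatment-emergent SAEs only, and its narrative commitment is limited in the same way: "Clinical narratives for each TESAE observed will be written to include important data and safety findings". The listing in SAP 10.2.3 is also restricted to treatment-emergent events. Only deaths (SAP 10.2.1) are listed and narrated without a time window.

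Protocol 11.5 is wider: "Summaries of treatment-emergent AEs (TEAEs) will include any AEs reported beginning with the first dose of study treatment on Day 1". It gives a start and no end. Protocol 9.7.3 collects AEs from consent to the final visit and adds: "Any AE that the investigator becomes aware of that occurs within 30 days of study completion or withdrawal should also be reported".

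SAP 12 shows that the cut-off was chosen deliberately: "The SAP was revised and amended to remove the 30 day window for the derivation of treatment emergent adverse events". It gives no reason. SAP 3.3 nevertheless states: "The analyses described in this analysis plan are consistent with the analyses described in the study protocol".

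**The concern.** The primary objective is long-term safety and tolerability. The protocol requires a taper and then a final visit with an AE assessment four weeks later. Under the SAP, no table shows how many subjects had an AE or SAE after stopping the drug. A reader of the study report would have to count them from a listing. Because AEs are recorded from consent, that listing also holds pre-dose events, including any from the de novo washout.

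The urinary assessment shows the gap. Protocol 9.6.2 names bladder effects as a potential risk and defines an AE by score: "An increase of 4 points in the total USP score from the previous visit will be considered an AE". A rise dated to the Week 60 visit, or to the recall period before it, would be in no AE table. SAP 10.6 summarises the USP sub-scores, not the total score that triggers the AE.

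Because SAP 3.3 declares no change, the reader is also not told that the tabulated window is narrower than Protocol 11.5 describes.

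**Working it through.** The plan states no figure to reproduce here. The check is schedule arithmetic, followed by tracing one event through the planned outputs.

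**Inputs**
- Taper: Weeks 54 to 56 (Protocol 7.5).
- Visit 6: Week 54 ±3 days. Visit 7, the end-of-taper telephone visit: Week 56 ±5 days. Visit 8, the final visit: Week 60 ±3 days (Protocol Table 1, 6.5, 6.6).
- AE reporting after study end: 30 days (Protocol 9.7.3).
- USP recall: 4 weeks (Protocol 9.6.2).

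**Length of the untabulated period for completers**
1. Nominal: (60 − 56) × 7 = 28 days.
2. Within the Visit 7 and Visit 8 windows: 28 − 5 − 3 = 20 days to 28 + 5 + 3 = 36 days.
3. Alternative, a 14-day taper counted from Visit 6 (±3 days): 28 − 3 − 3 = 22 days to 28 + 3 + 3 = 34 days.
4. Cross-check from the stated durations: 9 + 364 + 14 = 387 days of dosing. Week 60 is day 420, and 420 − 387 = 33 days, inside the range in step 2.
5. Share of the schedule: 28 / (60 × 7) = 28/420 = 6.7%.
6. With the 30-day reporting period: 28 + 30 = 58 days after the last dose. The last 30 of these have no scheduled assessment.

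**Subjects maintained only on 40 mg/day.** Protocol 7.1.1 says they have no taper phase; Protocol 7.5 and 12.4 make no such exception. If 7.1.1 means the end-of-treatment taper, their gap is (60 − 54) × 7 = 42 days, or 36 to 48 with ±3 days at each end (42/420 = 10%).

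**Early withdrawals.** No interval is set between the end of the taper and the early-termination visit, so their gap is not fixed.

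**USP example.** In Protocol Table 1 the first USP after Week 54 is at Week 60. Its recall reaches back to Week 60 − 4 = Week 56, the nominal end of taper.

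**Tracing a non-fatal SAE that starts the day after the last dose**

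| Output | Included? |
|---|---|
| TEAE tables, overall and by period (SAP 10.1) | No |
| Treatment-emergent SAE table (SAP 10.2.2) | No |
| SAE narrative (SAP 10.2.2) | None planned |
| Serious TEAE and discontinuation listing (SAP 10.2.3) | Not by this event |
| Listing of AEs that are not treatment-emergent (SAP 10.1) | Yes |

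**Scale.** At 28 days each, the untabulated follow-up is 50 × 28 / 365.25 = 3.8 person-years if 50 subjects complete, and 300 × 28 / 365.25 = 23.0 if all 300 planned subjects do. No event rate is given for this period, so these cannot be turned into event counts.

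**The case against.** The strongest defence is that an on-drug window is a legitimate choice and fits this plan. SAP 10.1 presents AE summaries by dose at the time of the event, and an event after the last dose has no such dose. Protocol 11.5 names no end point, so the SAP narrows open wording and contradicts no stated window. Protocol 9.7.3 governs collection, not tabulation. The cut-off is stated openly in SAP 10.1 and recorded in SAP 12. All of this stands. It justifies the on-drug tables, but it does not explain why no table covers the period after them.

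Much is also still reported: taper-period events in their own tables, on-drug events that continue, all deaths, and the Week 60 laboratory, vital-sign, ECG and USP sub-score summaries. An AE that leads to withdrawal before Visit 8 would contribute to the disposition reasons, and drugs given for it would enter the concomitant-medication table. SAP 10.6 allows further safety analyses after results are seen. None of these counts post-treatment AEs or SAEs by term, and the last is an option, not a plan.

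The USP example is conditional. The rise is measured from Week 54, so the interval includes the taper, and the documents give no rule for dating such an AE. If it is dated to the taper, it is tabulated.

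Finally, the study is single-arm and descriptive with no tests, and no on-drug rate is shown to be wrong. That limits the seriousness of the point but does not remove it.

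**Conclusion.** The concern holds and should be fixed. AEs and non-fatal SAEs with onset or worsening after the last dose reach one listing and no incidence table, and no narrative is planned for those SAEs. SAP 3.3 does not declare that the window is narrower than in Protocol 11.5.

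For completers who taper as scheduled, the period is nominally 28 days (20 to 36 within visit windows). This takes Week 56 as the last dose. The period would be about 42 days for 40 mg/day subjects if they have no end-of-treatment taper, and it is undefined for early withdrawals. The number of events left out is unknown. The on-drug tables are valid as they are; the defect is an omitted summary and an undeclared change.

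**What to change.** - **Tables.** Keep every on-drug table by dose and period. Add one SOC/PT table, or a post-treatment column, of AEs and SAEs with onset or worsening after the last dose through the end of AE collection, and at least to the Week 60 visit. Use as denominator the subjects with any follow-up after the last dose. Simply restoring last dose plus 30 days would cover the nominal 28 days but not the 36-day upper limit or the 42-day case.
- **Narratives.** Extend the planned SAE narratives to the same period.
- **SAP 3.3.** State the last-dose cut-off as a change from Protocol 11.5 and give the reason.
- **Start of the period.** Protocol 7.1.1 must be reconciled with 7.5 and 12.4 on whether 40 mg/day subjects have an end-of-treatment taper, so that the start of the post-treatment period is defined for them.

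The cost is one table or column, possibly a few more narratives and a sentence in SAP 3.3, all from data already collected. The downside is slightly higher reported AE counts, shown separately from the on-drug results.
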